2.2 Exhaled breath analysis by mass spectrometry

Analysis of exhaled breath gives biochemical information about the metabolism and the pathophysiological state. Chemical analysis of exhaled breath with mass spectrometry identified numerous volatile organic compounds (VOCs) [low molecular weight-components: < 500 Dalton (Da)].

The origin of these VOCs is diverse. VOCs can either be endogenous (arise from the respiratory tract), systemic (passing the blood-air barrier) or can be of exogenous origin (inhaled/exhaled environment air).⁽²⁾ The alveoli are intimately connected with the systemic circulation through the alveolar capillaries and its large blood-gas-interface. It was demonstrated that exhaled human breath contains a molecular fingerprint (also referred to as breathprint⁽⁹⁾). Breath composition changes during the course of the day (intra-individual variations). These temporal fluctuations may reflect circadian changes (13-15). Despite these changes, it was shown that each individual shows a distinct breathprint stable in time (individual core pattern of volatile and semi-volatile metabolites)⁽¹⁶⁾. The findings of preliminary studies by others and our group suggest that diseases of the airways such as e.g. chronic obstructive pulmonary disease

(COPD)(17, 18) may be diagnosed by a specific exhaled breath pattern.

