4.4 Recruitment, screening and informed consent procedure

Recruitment

COPD patients will be consecutively recruited from the wards at the University Hospital Zurich. The treating physician will approach patients via personal communication. If interested, the treating physician will inform one of the investigators who then will contact the patient.

Participants will not be offered any material compensation for their voluntary agreement to take part in this study (Art. 14 HFG). Whilst the scientific benefit from participation will be explained to participants, no other incentives will be offered.

Patient Information and Informed Consent

The investigators will explain to each participant the nature of the study, its purpose, the procedures involved, the expected duration, the potential risks and benefits and any discomfort it may entail. The right of the participant to refuse to participate without giving reasons will be respected, and withdrawal of consent will not affect the participant's subsequent medical assistance and treatment. In the event of withdrawal of the participant's consent, data collected up to the date of the withdrawal will remain coded in the study database.

The participant must be informed that his/her medical records may be examined by authorised individuals other than their treating physician. The date and time of the consent will be recorded by the investigator (or his designee) and it will be retained as part of the study records.

The participant information sheet and the consent form will be submitted with the protocol for review and approval for the study by the CEC. The formal consent of a participant, using the approved consent form, must be obtained before that participant is submitted to any study procedure.

The participant should read and consider the statement before signing and dating the informed consent form, and should be given a copy of the signed document. The consent form must also be signed and dated by the investigator (or his designee) and it will be retained as part of the study records.

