spectrometer by Thermo Fisher. This results in sensitive and selective, yet real-time, analysis of trace vapour species.(53) Our SESI-HRMS is situated in a separate, lockable room at the University Hospital Zurich. Access to the designated room is only permitted to members of the staff. Participants will be asked to refrain from eating, drinking, chewing gum, alcohol, tobacco, caffeine use or brushing their teeth at least 1 hour before the measurements will be performed. Room temperature and lighting will be set at the same level for all measurements. Participants will exhale through a disposable mouthpiece, into a heated tube (stainless steel, Silconert coated) (50 cm long, 4 mm in diameter) connected to the curtain AUX gas port of a Orbitrap spectrometer (Thermo Fisher, Waltham, Massachusetts, USA) that is provided by DBI. The sampling tube is surrounded with an isolated heating tape at 130 °C to prevent water condensation and to minimize losses of exhaled compounds onto the walls of the tube. While performing full exhalations, the subjects will keep the volume through the sampling line at 8L/min monitored by a digital flow meter. A nano electrospray plume (FIT, Madrid, Spain), provided by DBI, will be used, where compounds of exhaled breath get ionized and subsequently are mass analysed. The technique, by which breath is analysed in real time by injecting exhaled breath into electrospray plumes of pure solvent and thus causing ionization of relevant exhaled compounds(54-56), has been referred to as secondary electrospray ionization (SESI)(57). Breathprints will be collected in real-time recording six replicates through the mouthpiece. The raw mass spectra will be exported as mzXML files for further processing using MATLAB (Mathworks, Inc). The spectra of exhaled breath will be averaged. In this process, only the last few seconds (typically around 6 sec.) of each exhalation will be considered, thus the first part of the exhalation, which reflects mostly the dead space in the upper respiratory tract, will be excluded from the analysis. SESI-MS allows for real-time breath-printing by detection of both volatile and non-volatile trace components in breath without any sample pre-treatment. The de-identified mass spectrometric breath signatures of patients are subsequently analysed by DBI with AI algorithms for spectroscopic profiling.

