4.5.9 Study visits

Participation in the study requires two on-site study visits. Visit 1 will be performed while the participant is hospitalized. This visit will have a duration of approximately 45 minutes. After approximately 8 weeks patients are invited to the hospital to perform visit 2. This visit will take again approximately 45 minutes. Further information in Appendix.

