5. STATISTICS AND METHODOLOGY

5.1 Statistical analysis plan

For data processing, we will follow the same procedure as described in our previous studies [Gaugg, 2016]: raw mass spectra will be transformed to *.mzXML format using the online tool msConvert. The *.mzXML files will be imported into Matlab. Each mass spectrum is then interpolated (shape-preserving piecewise cubic interpolation method), mass calibrated using an iterative grid search algorithm, and the resulting spectra are centroided. To test the hypothesis that there is a significant difference in the values of exhaled metabolites during and after the exacerbation, we will perform a paired-sample t-test to

evaluate differential concentrations of such metabolites. False discovery rate and q-values will be subsequently computed as defined by Storey.(60) To account for instrumental drift (e.g., detector sensitivity), the mass spectra are normalized using standard methods such as interquartile range, total ion current. Well-established data reduction techniques such as principal component analysis will be used for visualization purposes. Finally, high mass resolution/high mass accuracy data obtained will allow us to query online databases (e.g., human metabolome database) to provide tentative identification of the subset of most informative exhaled compounds. The preprocessing of the raw mass spectra and the statistical analysis will be implemented using MATLAB (MathWorks, Massachusetts, US).

For correlation analysis, the Pearson's linear correlation coefficient and 95% bootstrap confidence intervals will be applied. Continuous data will be summarized by means (SD) or medians (quartiles) as appropriate. A two-sided p value of <0.05 will be considered to be statistically significant for all tests.

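### The protocol says breath composition varies over the day, but the hour of measurement is neither matched between visits nor used in the paired analysis

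*Combined protocol and SAP*

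**What the plan says.** All references are to the combined protocol and SAP.

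- **Section 2.2** states that "Breath composition changes during the course of the day (intra-individual variations") and adds, with a hedge, that "These temporal fluctuations may reflect circadian changes". It then says that, despite this, "it was shown that each individual shows a distinct breathprint stable in time", with reference to an individual core pattern.
- **Section 4.5.7** sets the measurement conditions: at least 1 hour without food, drink, tobacco and similar exposures, a fixed flow and a heated sampling tube. For the room it says "Room temperature and lighting will be set at the same level for all measurements". It does not mention time of day. Six replicate exhalations are recorded and the spectra are averaged.
- **Section 4.5.9** places visit 1 during the hospital stay. For visit 2 it says "After approximately 8 weeks patients are invited to the hospital to perform visit 2". The schedule in section 12 gives day 0 and 8 weeks, with no hour.
- **Section 4.4** has a clock time, but for consent only: "The date and time of the consent will be recorded by the investigator". That is the earliest time at which the visit 1 measurement can start. It says nothing about visit 2.
- **Section 5.1** gives the primary analysis: to compare metabolites "during and after the exacerbation, we will perform a paired-sample t-test", followed by Storey q-values. On normalisation it says "To account for instrumental drift (e.g., detector sensitivity), the mass spectra are normalized using standard methods such as interquartile range, total ion current".
- **Section 5.2** calls the study exploratory and sets 40 complete pairs without an effect size, SD or power.

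**The concern.** The protocol names a within-person source of variation in its own primary measurement and cites three references for it, yet the list of controlled conditions leaves it out. The primary contrast is a within-person difference between two occasions, so a within-person factor that differs between those occasions goes straight into it.

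No planned step removes it:

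- Pairing cancels what is constant in a patient, not a difference in hour between the two visits.
- The six replicates are described as one recording at each visit, so averaging them leaves a between-visit difference in hour untouched.
- Interquartile-range or total-ion-current normalisation is aimed at instrument drift and acts on the whole spectrum. It cannot remove a rhythm specific to one metabolite.
- q-values deal with multiplicity, not with extra variance in each test.

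What is at stake is sensitivity for rhythmic metabolites. If inpatient and return visits also fell at systematically different hours, a daily rhythm could look like an exacerbation effect. The documents leave that possible but do not show it.

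**Working it through.** **The plan's own figure.** N = 40 cannot be reproduced, because section 5.2 gives no effect size, SD or power. As a reference, a paired t-test with n = 40 and two-sided 0.05 (section 5.1) has 86.9% power for a standardised mean change d_z = 0.5 (noncentral t). The d_z is an assumption.

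**Assumptions for the rhythm.** None of these is in the documents.

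- The metabolite follows a 24-hour cosine with amplitude A, in within-person SDs. A = 0.25, 0.5 and 1.0 are tried.
- Each visit's hour is independent and uniform over a window of W hours.
- With matched hours the paired difference has variance 2, that is, two independent within-person errors of variance 1.
- Results are averaged over the phase of the rhythm.

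**Added variance.** Two independent visit hours add 2·Var[A cos(2π(t − p)/24)]. The phase average is A²·[1 − (sin x / x)²] with x = πW/24. Dividing by 2 gives the relative rise r.

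For W = 10 (08-18 h), x = 1.309 and 1 − (sin x / x)² = 0.4555. So r = 0.25 × 0.4555 / 2 = 5.7% at A = 0.5, and 0.4555 / 2 = 22.8% at A = 1.0.

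**Power.** d_z becomes 0.5/√(1 + r). For example, 0.5/√1.2277 = 0.451.

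| Window | r at A = 0.25 / 0.5 / 1.0 | Power at A = 0.25 / 0.5 / 1.0 |
|---|---|---|
| 4 h | 0.3% / 1.1% / 4.4% | 86.8% / 86.6% / 85.5% |
| 6 h | 0.6% / 2.4% / 9.5% | not tabulated |
| 8 h | 1.0% / 4.0% / 15.8% | not tabulated |
| 10 h | 1.4% / 5.7% / 22.8% | 86.5% / 85.1% / 79.5% |

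In pairs, the 10-hour window is like having 40/1.0569 = 37.8 pairs at A = 0.5, or 40/1.2277 = 32.6 pairs at A = 1.0.

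**If patients also differ in their true change.** Suppose this doubles the variance of the difference to 4, with baseline d_z kept at 0.5. The added share then halves. For A = 0.5 or 1.0 it is 0.6% or 2.2% over 4 h, and 2.8% or 11.4% over 10 h. Power over 10 h is 86.0% or 83.2%.

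**With booking.** If the visit 2 hour equals the visit 1 hour plus a uniform error within ±1 h, the rise is A²·[1 − sin(w)/w]/2 with w = 2π/24. That is 0.14% at A = 0.5 and 0.57% at A = 1.0.

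**Without booking, matching by chance.** P(hours within 1 h) = 1 − (1 − 1/W)². For W = 10 this is 1 − 0.9² = 0.19, or 7.6 of 40 pairs. For W = 4 it is 1 − 0.75² = 0.4375, or 17.5 of 40. Power for d_z = 0.5 in such a subset is 23% at n = 8 and 52% at n = 18.

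**Systematic offset (conditional illustration only).** If visit 2 fell 3 h later or earlier for everyone and all patients shared one peak time, the spurious |d_z| would lie between 0 and 2A·sin(3π/24)/√2. The upper limit is 0.27 at A = 0.5 and 0.54 at A = 1.0. If peak times vary between patients with an SD of 4 h, the mean shift is multiplied by exp(−(2π·4/24)²/2) = 0.578. The limit, allowing for the extra spread, becomes 0.16 or 0.30. With the difference variance doubled as well, it is 0.11 or 0.22.

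**The case against.** The strongest case against is that the effect may not matter. At A = 0.5 the power loss is 0.3 points over 4 h and 1.8 points over 08-18 h. At A = 0.25 it is negligible. Only a strong rhythm (a peak-to-trough swing of two within-person SDs) with a wide spread of hours gives a visible loss, and variation between patients in the true change shrinks it. Amplitude, hours and the share of rhythmic metabolites are all assumed. Section 2.2 is hedged and also describes a stable individual pattern. The study is exploratory, with no power target to miss. Random differences in hour lower sensitivity but do not create false signals. Section 8.1 refers to written SOPs, and Figure 2 is not visible, so the hour may already be set elsewhere. A narrow booking slot could also deter recently hospitalised patients from returning.

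Most of this stands, and it limits how strongly the point can be put. It does not close the gap. The stable core pattern does not mean that single metabolites lack a rhythm, and single metabolites are what the t-test examines. If an SOP sets the hour, the protocol only needs to say so. The worry about attendance is met by making the target apply where feasible. The restricted re-analysis does add little once visits are booked, since most pairs should then fall within the window.

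**Conclusion.** The concern holds. The protocol recognises variation over the day, and no visible section matches, restricts, records or adjusts for the hour of breath acquisition. The consequence is avoidable noise in the primary contrast for rhythmic metabolites. Its size cannot be fixed from the documents. Over the assumed range the variance of the paired difference rises by between 0.3% (A = 0.25, 4 h) and 22.8% (A = 1.0, 08-18 h), or less if the true change varies between patients. Bias is a possibility only and should not be claimed.

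This is a worthwhile improvement, not a flaw that invalidates the study. Confidence is medium, because the effect may be small and an SOP that cannot be seen here may already cover it. The case rests on the low cost and on timing: hours can be matched only before the measurements are made, and selecting matched pairs afterwards would leave about 8 to 18 of 40.

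**What to change.** **Sections 4.5.7 and 4.5.9.** Add a sentence such as: *The visit 2 breath measurement is booked at about the same clock time as the participant's visit 1 measurement (target within 1 hour where feasible), and acquisition time is recorded at both visits.* If an SOP already does this, cite it instead. The 1-hour target is a judgement. Visit 2 is the easier visit to time, because inclusion at visit 1 is tied to less than 48 hours after treatment starts (section 4.2).

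**Section 5.1.** Report the distribution of the clock-time difference between visits 1 and 2, which lets readers check for a systematic offset. As a sensitivity analysis only, repeat the primary contrast in pairs measured within the window.

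**Cost.** One scheduling sentence, one recorded field, one reporting line and a simple re-run of the primary test. The price is slightly less flexible booking of visit 2. No procedure, visit or staff is added.

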4.5.8 Questionnaires

4.5.8.1 COPD Assessment Test (CAT) & modified Medical Research Council (mMRC)

For assessing symptoms, GOLD guidelines primarily recommend the use of the COPD Assessment Test (CAT) or the modified Medical Research Council (mMRC) dyspnea score. The CAT score is a patient-completed instrument to assess and quantify health-related quality of life and symptom burden in COPD patients. It comprises 8 questions, each is presented as a semantic 6-point (0-5) differential

scale, providing a total score out of 40. Scores of 0-10, 11-20, 21-30, 31-40 represent mild, moderate, severe or very severe clinical impact, respectively. The mMRC dyspnea score is a 5-point (0-4) scale based on the severity of dyspnea.(58)

4.5.8.2 QUIT

QUIT is a Questionnaire to assess the probability of therapy adherence, especially in inhaled therapies. The Test was developed by the healthcare research unit of the Federal Association of Pneumologists in Germany. The Questionnaire was initially designed with focus on asthma patients. In COPD the adherence to inhalational therapy is much higher due to the consistency of symptoms during the disease progression. We use an adapted version with focus on COPD therapy.(59)

4.5.9 Study visits

Participation in the study requires two on-site study visits. Visit 1 will be performed while the participant is hospitalized. This visit will have a duration of approximately 45 minutes. After approximately 8 weeks patients are invited to the hospital to perform visit 2. This visit will take again approximately 45 minutes. Further information in Appendix.

4.5.10 Study duration

Individual participation time in this study will be approximately 8 weeks. Overall recruitment of patients will last until the targeted sample size is reached.

4.6 Withdrawal and discontinuation

Consent withdrawal of the patient will lead to an exclusion of the study. Data obtained up to the withdrawal will be included for the analysis.

5. STATISTICS AND METHODOLOGY

5.1 Statistical analysis plan

For data processing, we will follow the same procedure as described in our previous studies [Gaugg, 2016]: raw mass spectra will be transformed to *.mzXML format using the online tool msConvert. The *.mzXML files will be imported into Matlab. Each mass spectrum is then interpolated (shape-preserving piecewise cubic interpolation method), mass calibrated using an iterative grid search algorithm, and the resulting spectra are centroided. To test the hypothesis that there is a significant difference in the values of exhaled metabolites during and after the exacerbation, we will perform a paired-sample t-test to

evaluate differential concentrations of such metabolites. False discovery rate and q-values will be subsequently computed as defined by Storey.(60) To account for instrumental drift (e.g., detector sensitivity), the mass spectra are normalized using standard methods such as interquartile range, total ion current. Well-established data reduction techniques such as principal component analysis will be used for visualization purposes. Finally, high mass resolution/high mass accuracy data obtained will allow us to query online databases (e.g., human metabolome database) to provide tentative identification of the subset of most informative exhaled compounds. The preprocessing of the raw mass spectra and the statistical analysis will be implemented using MATLAB (MathWorks, Massachusetts, US).

For correlation analysis, the Pearson's linear correlation coefficient and 95% bootstrap confidence intervals will be applied. Continuous data will be summarized by means (SD) or medians (quartiles) as appropriate. A two-sided p value of <0.05 will be considered to be statistically significant for all tests.

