Investigators from University Hospital Zurich	
[name]. med. [name], Pulmonary Division, University Hospital Zurich, [name], Switzerland. [contact]
 
[name], RPh, Pulmonary Division, University Hospital Zurich, [name], Switzerland. [contact]
 
[name], Pulmonary Division, University Hospital Zurich, [name], Switzerland. [contact]
 
[name], Pulmonary Division, University Hospital Zurich, [name], Switzerland. [contact]

Study Centre	Pulmonary Division, University Hospital Zurich, [name], Switzerland
Statistical Considerations	
To test the hypothesis if there is a significant difference in the values of exhaled metabolites during and after COPD exacerbation, we will perform a paired-sample t-test to evaluate differential concentrations of such metabolites. False discovery rate and q-values will be subsequently computed as defined by Storey.(7) Well-established data reduction techniques such as principal component analysis will be used for visualization purposes. Finally, high mass resolution/ high mass accuracy data obtained will allow us to query online databases (e.g., human metabolome database) to provide tentative identification of the subset of most informative exhaled compounds. The pre-processing of the raw mass spectra and the statistical analysis will be implemented using MATLAB (MathWorks, Massachusetts, US).

GCP Statement	
This study will be conducted in compliance with the protocol, the current version of the Declaration of Helsinki(8), the principles of Good Clinical Practice and as well all national legal and regulatory requirements in Switzerland.

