2.5 Exhaled breath analysis in COPD

Breath analysis in COPD is attractive because breath is available in nearly unlimited quantities. The analysis is non-invasive, and it presents no burden to the subject being measured. On-line breath analysis in COPD would allow continuous monitoring of metabolic health, disease progression, and medication in short time intervals. Data are obtained immediately which is of high importance in situations like COPD exacerbations.(2)

The diagnostic “gold standard” for COPD is based on spirometry and subjective symptom assessments, similar to asthma with respective COPD guidelines.(29) As it is primarily a disease of the lungs, a high number of breath-analysis studies are available for COPD; however, only a minority of the studies employed on-line methods.(30) Most studies used a case-control design with an untargeted approach in order to identify putative discriminative markers for the disease or disease severity. Three studies used ion mobility separation to identify COPD-specific biomarkers in a cohort of 119, 130, and 96 patients, respectively.(31-33) While two studies reported a 70–79% accuracy in the diagnosis of COPD (based on 6–10 VOCs), the other study reported 10 biomarkers, most of which were unidentified.(31) None of the identified substances overlapped between the two studies or was validated in an external cohort. Finally, two untargeted studies (17, 18) compared the breath print of COPD patients against healthy controls using SESI-MS with a real-time approach. Both studies yielded a Receiver Operating Characteristic (ROC) curve with an area under the curve of 0.88–0.91. However, in this case, with the aid of MS/ MS and complementary pre-separation methods some of the discriminate biomarkers could be identified and attributed to be metabolites of oxidative stress processes, such as fatty acids,

aldehydes, and amino acids.(17, 18) Most studies tried to control for the effects of smoking and there was evidence that lung capacity, body mass index, and certain inflammatory blood markers seem to play a role in the discrepancies observed between groups.(33, 34) In conclusion, studies on this topic are extremely heterogeneous and data processing and statistical methods are not standardized. As a result, none of the reported biomarkers overlaps between the studies and none of the biomarkers has been validated in an external cohort yet.

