3.2.2 Secondary Outcome Measures

Correlation of breath metabolites with symptoms (mMRC and CAT®), inflammation markers (CRP and eosinophils, exhaled NO), causative agents (sputum microbiology and viral swabs) and treatment (inhalational drugs, steroids, antibiotics).

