7. FURTHER ASPECTS

7.1 Overall ethical considerations

This will be the first study to investigate the acute effects of COPD exacerbations on molecular exhaled breath patterns assessed by SESI-HRMS. By identifying a distinctive breath pattern it may be possible to define biochemical processes specific of a COPD exacerbation and correlate it with causative agents, treatment and outcome. It may also be possible to identify those patients who need, and are most likely to respond to additional therapy such as e.g. antibody treatment.

The study procedure (contact to patients and relatives) will be conducted in accordance with internationally accepted quality criteria and entails only minimal risks and burdens.

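### As written, the secondary breath-to-clinical correlations are called significant at an unadjusted p<0.05, because q-values are attached only to the paired t-test

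*Combined protocol and SAP*

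**What the plan says.** The primary analysis in section 5.1 is a paired t-test for each metabolite, followed by: "False discovery rate and q-values will be subsequently computed as defined by Storey". The synopsis (Statistical Considerations) makes the same pairing, "to evaluate differential concentrations of such metabolites. False discovery rate and q-values will be subsequently computed as defined by Storey", and gives no method for correlations.

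The correlations have their own later paragraph in section 5.1: "For correlation analysis, the Pearson's linear correlation coefficient and 95% bootstrap confidence intervals will be applied". That paragraph ends: "A two-sided p value of <0.05 will be considered to be statistically significant for all tests". It also says "Continuous data will be summarized by means (SD) or medians (quartiles) as appropriate", so the plan expects that some data may not suit means and SDs.

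Section 3.2.2 lists what is to be correlated with breath metabolites. There are two symptom scores (mMRC, CAT), three inflammation markers (CRP, eosinophils, exhaled NO), and "causative agents (sputum microbiology and viral swabs) and treatment (inhalational drugs, steroids, antibiotics". That makes ten named variables. Section 5.2 calls the study exploratory and fixes 40 complete pairs. No section states a feature count or a q-value threshold.

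**The concern.** The plan treats one test per feature as enough multiplicity to need false discovery control in the primary comparison. The secondary analysis can repeat those tests for up to ten clinical variables, yet has only the general 0.05 rule. The bootstrap intervals do not help here: each describes one correlation and takes no account of how many were examined.

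Section 7.1 hopes to tie breath patterns to causative agents, treatment and outcome, and says it may be possible to "identify those patients who need, and are most likely to respond to additional therapy". Those hopes rest largely on the secondary associations. Section 2.5 reports that in this field "none of the reported biomarkers overlaps between the studies and none of the biomarkers has been validated in an external cohort yet". A secondary list with many chance findings would make replication harder still.

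**Working it through.** **Inputs from the documents:** n = 40 complete pairs (5.2); two-sided 0.05 for all tests (5.1); ten named variables (3.2.2). The sample size is not derived from a formula and no error rate is given for the correlations, so there is no plan figure to reproduce.

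**Assumptions:** 20, 100 or 1,000 features; independent features, or features correlated up to 0.5; Storey's method with lambda 0.5; effect sizes and skewness as stated below.

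**Step 1. What passes at p<0.05.** The critical value is r = t/√(38 + t²) with t = 2.024 on 38 df, so |r| ≥ 0.312.

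**Step 2. Expected chance hits for one null variable** = 0.05 × features:
- 20 features: 1
- 100 features: 5
- 1,000 features: 50

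Correlation among features leaves these means unchanged but makes the count more variable.

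**Step 3. Chance of at least one false hit for one null variable.** With independent features this is 1 − 0.95^m: 64% for m = 20, 99.4% for m = 100, and essentially 100% for m = 1,000. Simulation with Spearman's correlation, from independent features to correlation 0.5:

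| Features | p<0.05 | q<0.05 |
|---|---|---|
| 20 | 44–66% | 6–10% |
| 100 | 80–100% | 6–8% |
| 1,000 | over 99% | 6–8% |

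**Step 4. Effect when some associations are real.** 1,000 independent features, 50 truly associated, Spearman; entries are true / false hits:

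| Rule | r = 0.5 | r = 0.4 |
|---|---|---|
| p<0.05 | 44.3 / 47.8 | 34.4 / 47.9 |
| q<0.05 | 22.9 / 1.5 | 7.0 / 0.6 |
| q<0.10 | 28.7 / 3.7 | 11.1 / 1.6 |
| q<0.20 | 35.0 / 9.6 | 17.4 / 5.3 |

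At p<0.05 the false share of the list is 47.8/92.1 = 52% for r = 0.5 and 47.9/82.3 = 58% for r = 0.4.

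**Step 5. Does Pearson's r matter?** With marker and feature both log-normal (log-SDs 0.7 and 1.0, or 1.0 and 1.2), Pearson's per-test rate at p<0.05 stays near 5% (4.9–5.2%). The problem lies in the far tail, which q-values use. If q-values are computed from Pearson p-values on such data, the chance of any q<0.05 hit for a null variable is 33–54% (100 features) or 57–81% (1,000). Spearman gives 6–8%, and Pearson on log-transformed intensities about 4–7%. If only the feature is skewed, Pearson holds at about 5–6%.

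**Step 6. Rare agents.** With k of 40 positive, the smallest exact two-sided rank-sum p is 2/C(40,k):
- k = 1: 2/40 = 0.05, so p<0.05 is impossible.
- k = 2: 2/780 = 0.0026. A lone hit over 100 features has q ≈ 0.26.
- k = 3: 2/9,880 = 0.0002. A lone hit over 1,000 features has q ≈ 0.20; over 100 features it is about 0.02.
- k = 4: 2/91,390 = 0.00002. A lone hit over 1,000 features has q ≈ 0.02.

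These q figures take the null proportion as 1.

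**The case against.** **Silence is not exclusion.** No sentence says that the correlations are left out of false discovery control, and the 0.05 rule also nominally covers the primary t-tests. A reader might infer that the sponsor deliberately decided the primary on q and the secondaries on p. The documents do not show that, since no q threshold appears anywhere. It remains true that nobody following the text would know to adjust the correlations.

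**The breadth of testing is assumed.** A reader might infer hundreds of false findings: ten variables by 1,000 features would give 500 under a complete null. No section says that every feature is correlated with every variable. Section 8.4 describes the collaborator's analytics and offers a targeted subset as well as the full spectrum. Every patient is on triple therapy, so inhaled treatment does not vary at class level. That total is therefore not established. The per-variable figures survive, because even 20 correlated features give about a 44% chance of a false hit.

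**Pearson is not itself the error.** A reader might infer that skewed data invalidate the plan's tests. At p<0.05 they do not (step 5). For a yes/no factor Pearson is equivalent to a t-test. Sections 3.1.2 and the synopsis speak of association as well as correlation, so the plan need not be read as applying Pearson to unordered organisms. The method matters only once q-values are computed. The processing follows earlier studies not available here, so intensities may already be transformed.

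**The study is exploratory.** This lowers the stakes. However, the plan does not label the correlations descriptive; it provides for calling them significant. Section 2.5 links the lack of overlap to heterogeneous studies and unstandardised methods, not to multiplicity, so it is context rather than proof.

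**Conclusion.** The point holds for the secondary, exploratory associations and should be corrected. Under the rule as written, about 5% of null feature-by-variable tests are called significant: about 1, 5 or 50 per null variable at 20, 100 or 1,000 features. If 5% of 1,000 features are truly associated at r = 0.4 to 0.5, somewhat more than half of the resulting list is false. These sizes rest on assumed feature counts and effect sizes. The 5% rate itself does not.

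The primary comparison is not undermined, since it already has q-values, although its threshold also needs stating. Nothing here shows that the choice of Pearson inflates the plan's own p<0.05 test.

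**What to change.** Add to section 5.1 wording such as:

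> Storey q-values will also be computed for the secondary associations, within each clinical variable over all features tested. An association is called significant on its q-value, at a threshold stated here for both the primary and secondary analyses. The q-value is reported for every feature, and bootstrap intervals are descriptive.

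Then:
- Limit the 0.05 rule to tests that have no q-value.
- Compute the q-values from Spearman's correlation or from log-transformed intensities.
- Analyse causative agents and treatments as present/absent comparisons. Report descriptively any agent too rare to reach the threshold (about 3 or fewer of 40, depending on the feature count).

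Labelling the correlations descriptive, with no significance claims, would also remove the problem.

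**Cost.** SAP wording and a few lines of code; no new data. The hit list shortens as in step 4, sharply at r = 0.4 (7 of 50 true associations found at q<0.05, against about 34 at p<0.05). A looser threshold recovers some, and reporting every q keeps weaker signals visible. With normal data Spearman has about 5 points less power than Pearson at r = 0.4 (69% against 74%, unadjusted).

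Control within each variable is not complete. Of ten null variables, 0.6–0.8 on average would still show a false hit, against 8–10 at p<0.05 (100 or more features). With strongly correlated features the false hits cluster: the mean per null variable can reach 2.6 (100 features) or 25 (1,000), against 5 and 50.
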